4. A urology resident admits the patient to the hospital and makes sure that cardiac and other pre-transplant evaluation information is up to date. The resident ensures that the patient does not have a history of recent infection, newly diagnosed cancers, recent cardiac events or newly diagnosed vascular complications.
5. The transplant surgeon evaluates the recipient and consents them to use Campath® in an off-label fashion as the immunosuppressive induction agent either as part of the study described herein or as part of the standard of care.
6. The patient is pre-medicated with:
 - a. Tylenol® 650 mg PO
 - b. Benadryl® 25 mg IV
 - c. Pepcid® 20 mg IV
 - d. Methylprednisolone 500 mg IV

- e. myfortic® 540 mg PO
7. Following the pre-medication above, the patient is administered Campath® over 2-3 hours. The dose is 0.5 mg/kg for patients up to the weight of 60 kg. Any patient whose weight is ≥ 60 kg is given a total dose of 30 mg Campath® intravenously. Only one dose of Campath® is given on Day 0.
8. Patients are to be observed closely for the possibility of a cytokine release response, although this response is much less frequent with Campath® than has been observed with OKT3®.
9. The renal transplantation operation is then performed with the goal of completing the Campath® infusion prior to removing the arterial vascular clamps and re-establishing blood flow to the transplanted kidney.
10. Just prior to removing the arterial vascular clamps, 40 mg of Lasix® and 12.5 grams of mannitol will be administered IV.
11. Post-operatively, during hospitalization (expected to last 4-5 days), the following medications are initiated:
 - a. Tacrolimus 0.15 mg/kg PO BID adjusted to achieve a target (serum level of 10 ng/ml).
 - b. myfortic® 540 mg PO BID is initiated and adjusted for diarrhea or leukopenia defined as a WBC < 1.0 or an absolute neutrophil count < 500 .
 - c. Valcyte® 450 PO mg daily for CMV-mismatched recipients or 450 mg PO every other day for non-CMV-mismatched recipients.
 - d. Bactrim® DS one tab PO daily for PCP prophylaxis.
 - e. Mycelex® Troche one troche PO QID.
 - f. Flagyl® 500 mg PO TID to prevent Clostridium difficile infection.
 - g. The following steroid taper will be followed:
 - i. Post-op day 1: Prednisone 250 mg PO daily.
 - ii. Post-op day 2: Prednisone 125 mg PO daily.
 - iii. Post-op day 3: Prednisone 60 mg PO daily.
 - iv. Post-op day 4: Prednisone 30 mg PO daily.
 - v. Post-op day 5: Prednisone 15 mg PO daily.
12. If delayed graft function is suspected, tacrolimus may be held for the first few days until the creatinine level begins to fall spontaneously.
13. Target tacrolimus levels for the first 2 months post-operatively will be 10-12 ng/ml with a target level goal of 10 ng/ml. After three months, the standard of care approach calls for the tacrolimus target level to be reduced to 8-10 ng/ml (with a target level of 8 ng/ml) until the end of the first year. After the first year, patients without evidence of rejection would have their tacrolimus dose reduced to achieve a trough level of 6-8 ng/ml (with a target level of 6 ng/ml). This approach was used for patients in the historical control arm.
14. No patients are to be treated for rejection without first obtaining a renal biopsy to confirm a cellular or humoral rejection.
15. Cellular rejections scored as Banff 1 will be treated with three, daily pulses of 250-500 mg methylprednisolone on three consecutive days and by confirming a therapeutic level of tacrolimus. Cellular rejections scored as Banff 2 or for those rejections that are not responsive to steroids alone, Thymoglobulin® will be used for a 10-14 day course. Depending on the level of rejection,

- ongoing steroid therapy can be administered after agreement by the treating physicians. Generally, hospitalization is required for at least the first few days of the treatment of rejection using Thymoglobulin®. During the first dose of Thymoglobulin®, blood pressure and vital signs will be monitored every 15 minutes for the first hour, then every 30 minutes for the next two hours, then every one hour for the next 3 hours and then per routine protocol if stable.
16. Humoral rejections will be treated with IVIG 100 mg/kg followed by a one volume exchange plasmapheresis on an every other day basis until the creatinine begins to fall or a decision is made to hold off on further treatment. In extreme cases, re-dosing Campath® can be considered or use of the anti-B cell agent, Rituximab (anti-CD20) can be used. These decisions will be made after consultation between the transplant surgeon and attending nephrologists.
 17. The intention-to-treat concept will be applied to patients who experience biopsy-proven rejection to avoid missing outcomes. For patients in the study, low-dose myfortic® may be added back to the patient's immunosuppression regimen. Short-term treatment with oral corticosteroids may be required, but long-term steroid use will be avoided.
 18. For patients with elevated, post-transplant creatinine but without biopsy proven evidence of cellular or humoral rejection, causes of elevated creatinine other than rejection should be considered. These include intercurrent illness, dehydration, BK-nephropathy and tacrolimus toxicity. Dose reduction of tacrolimus can be attempted to assess for the possibility of calcineurin-inhibitor nephrotoxicity. If dose reduction of tacrolimus is not acceptable, then everolimus (first choice) or Neoral® (second choice) will be used as replacement therapy.
 19. Upon discharge from the hospital, all patients will be treated with the following prophylactic medications:
 - a. Valcyte® 450 mg PO daily to prevent subsequent CMV infection (unless leukopenia or other side effects warrant further dose reduction or discontinuation). Valcyte® will be administered for 6 months if there is no CMV mismatch and for 12 months if there is a CMV mismatch.
 - b. Bactrim DS® one tablet PO Monday, Wednesday and Friday to prevent subsequent pneumocystis carinii pneumonia. In hospital desensitization with [name] can be performed if the patient has a known sulfa allergy or Dapsone replacement can be used. Bactrim® will be administered for at least one year following transplantation. Length of therapy after one year will be determined by physician and patient preference.
 - c. Mycelex® Troche one lozenge PO QID to prevent oral thrush. Mycelex troche® therapy will be continued for 6 months post-transplantation.
 - d. Flagyl® 500 mg PO TID to prevent Clostridium difficile infection only during in-hospital stays of transplant patients.
 20. BK viral titers will be assessed at three month intervals for the first year post-operatively.
 21. Post-transplant PRAs (to determine the presence or absence of donor specific antibodies – DSA) will be assessed at the patient's screening visit, at three month intervals for the first year post-operatively and every 6 months in the

second year post-operatively. PRAs may also be assessed at the discretion of the principal investigator or measured as part of the patient's standard of care/routine treatment.

22. For patients who are prescribed myfortic® as part of an intention-to-treat adverse event, MPA levels will be assessed on an as needed basis.
23. Patients who have CMV-mismatched kidneys may be followed with CMV viral titers. Patients suspected of rejection episodes due to elevated creatinine levels should also be assessed for the possibility of BK-nephropathy by following urine cytology, looking for viral inclusion bodies on electron microscopy of biopsy specimens and by following BK viral titers in urine and or blood.

Conversion at 2-6 Months (± 10 days) to the Study Protocol

1. Only patients who have reached the two month (± 10 days) post-operative mark without prior evidence of rejection will be offered the opportunity to participate in the study.
2. At the two month mark (± 10 days), patients will be counseled about participation in the study and informed consent obtained prior to participation. Our control group will consist of a historical control; prospective patients who are not willing to participate in the study will not be considered part of the control group.
3. Study participants will be maintained on the following immunosuppression regimen:
 - a. Their myfortic® will be weaned off quickly and everolimus initiated to achieve a target level of 3-8 ng/ml with a mean of 6 ng/ml. Once achieving a therapeutic dose of everolimus, the tacrolimus dose will be reduced to target a level of 3-5 ng/ml with a mean of 4 ng/ml.
 - b. As noted above, patients in the historical control group will have remained on tacrolimus and myfortic® according to the target levels outlined in #13 above. Briefly, the tacrolimus target level would be reduced to 8-10 ng/ml (with a target level of 8 ng/ml) until the end of the first year and after the first year the tacrolimus target level would be further reduced to 6-8 ng/ml (with a target level of 6 ng/ml) if no evidence of rejection had been encountered.

AE Reporting

Any suspected serious adverse event (SAE) will be reported to the Novartis drug safety and epidemiology team overseeing the study within 24 hours of investigator awareness that an SAE has occurred. An SAE report form will be completed for any serious adverse event occurring after the subject has provided informed consent and until 4 weeks after the subject has stopped study participation. A serious adverse event (SAE) report form will be faxed to the number provided by the Novartis clinical trials team.

The form will contain the following information:

Investigator contact details

Date of report
Subject description/study number / initials
Subject treatment arm
Study commencement date for subject
Subject information - date of birth, sex, ethnicity, height and weight
Subject's past medical history
Subject's current immunosuppressive regimen and dosages
SAE description
Narrative description of the SAE and details of drug and non-drug treatment
Onset Date and either Ongoing or End Date
Concomitant medications
Seriousness criteria (see below)
Outcome (Death, Recovered or Recovered with Sequelae)
Relationship to immunosuppressive medication regimen (suspected, not suspected or unknown).
Assessment of causality including alternative explanations and consideration of any co-suspect medications based on the data available at the time.
Signature of investigator

Clinically significant follow-up information and/or new data that has become available will be faxed to Novartis within 24 hours of the investigator becoming aware that it is available. It will be indicated whether the new information should be added to the previously reported information or should replace the previously reported information. The report type will be labeled as "initial" or "follow-up". Any SAEs that occur which are not associated with a previous report will require a new SAE report form.

Seriousness criteria (as per Novartis established definitions)

1. Death: *The subject died.*
2. Life-threatening: *The reporter believes the subject was at immediate risk of Death from the event as it occurred, e.g. aplastic anemia, anaphylaxis with peripheral circulatory collapse, suicide attempt by taking an excessive amount of study treatment. It does not include an event that, had it occurred in a more severe form, might have caused death.*
3. Required or prolonged inpatient hospitalization: *The subject had to be admitted to hospital as an in-patient or hospitalization of the subject had to be extended as a result of an AE.*

An SAE form will not be completed if the hospitalization:

- was for routine treatment or monitoring of the studied indication, not associated with any deterioration in condition
- involved treatment, which was elective or pre-planned, for a pre-existing condition that is unrelated to the indication under study and did not worsen
- was for general care, not associated with any deterioration in condition
- involved only treatment on an emergency, outpatient basis for an event not fulfilling any of the other definitions of serious and not resulting in hospital admission.

4. Resulted in persistent or significant disability/incapacity: *The event results in a substantial disruption of a person's ability to conduct normal life functions. The extent of the disability does not need to be permanent.*

5. Congenital anomaly / birth defect: *Any anatomical malformation or organ malfunction occurring in the offspring of a trial patient or subject.*

6. Other significant medical events: *Medical and scientific judgment should be exercised in deciding whether expedited reporting is appropriate in other situations, such as important medical events that may not be immediately life-threatening or result in death or hospitalization but may jeopardize the subject or may require intervention to prevent one of the other outcomes listed above. There may be other events judged to be medically serious or which are significant by specification in certain clinical trials.*

Suspected transmission of an infectious agent via a medicinal product should always be considered serious and assessed as medically significant in the absence of any other seriousness criteria. Cases of newly diagnosed cancer must be reported on a SAE form under 'other significant medical events' or hospitalization, death etc as appropriate. Cases of overdose which are life-threatening or result in death, hospitalization, significant disability or are considered medically significant should be reported on a SAE form. Overdose without clinical manifestation or leading to non-serious adverse events should not be reported on a SAE form.

Any AE, SAE or unanticipated problem occurring as a part of this trial that is considered related or possibly related to the patient's study treatment (immunosuppressive regimen) will also be reported to the University of Toledo Biomedical IRB Department for Human Research Protections on their corresponding internal adverse event reporting form within 7 days of the investigator becoming aware of the event as required by policy and in conformance with HHS and FDA regulations. Any pregnancies will be reported to Novartis within 24 hours of the investigator becoming aware of it.

The University of Toledo Biomedical IRB will have the authority to terminate IRB approval of research that is associated with unexpected serious harm to subjects.

Statistical Section:

This will be a small, pilot study to test whether conversion to everolimus (Zortress®), allowing the reduction of calcineurin inhibitors, will reduce nephrotoxicity (measured by increased creatinine clearance) and lengthen overall graft survival (measured by 2-3 year graft survival). As it is not a large study (55 patients, 11 patients per year), it is not powered to achieve statistical significance. The statistical significance will also be impaired by the use of a historical control group. However, the data generated will be published irrespective of the results, thus making the data available for meta-analysis.

This trial is designed as a parallel-group study. Analysis of data for this design is simple and interpretation of the result is straightforward. Given the limited number of

patients in the trial it may not be meaningful to apply analysis of (co)variance for the statistical evaluation of a continuous variables such as creatinine clearance, but we will attempt to use this method with the guidance of our statistician, [name].^{19,20} Likewise, the limited number of patients in the trial may prevent meaningful analysis of time-to-event variables such as graft survival. Nonetheless, we will work with [name] to use methods appropriate for survival analysis including the Kaplan-Meier method and Cox's proportional hazards regression to see if meaningful differences exist between our study groups and our historical control.^{21,22} If warranted, for safety analyses the AEs and SAEs could be summarized by treatment group but no statistical tests performed due to the population size as a pilot study. In addition, the PI and Co-PI will meet with other members of the clinical transplant team to review the results of this study on a quarterly basis to ensure that no significant adverse events warrant the discontinuation of the trial. Given the small number of patients in the trial, we will analyze the data after we have enrolled 10 patients. If the study immunosuppression regimen has a > 40% Banff 2a rejection rate or greater than 20% patient death rate, then that arm will be prematurely terminated. Serious adverse events will also be analyzed and may serve as grounds for study discontinuation.

Everolimus IIRP Pilot Study Evaluation and Visit Schedule

Treatment Period															
			Months												
	Screening (Visit 1)	Baseline (Visit 2)	1 (3)	2 (4)	3 (5)	4 (6)	5 (7)	6 (8)	9 (9)	12 (10)	15 (11)	18 (12)	21 (13)	24 (14)	
VISIT TIME WINDOWS	2-6 Mos ± 10 days		±7 days						±14 days			±30 days			
INFORMED CONSENT	X														
BACKGROUND INFORMATION	X														
MEDICAL HISTORY	X														
INCLUSION/EXCLUSION CRITERIA	X														
TRANSPLANT INFORMATION	X														
VIRAL SEROLOGY	X														
BK VIRAL TITERS			X		X			X	X	X		X		X	
EBV VIRAL TITERS (if neg)	X							X		X		X		X	
CMV VIRAL TITERS (if neg)	X														
DSA EVALUATION	X		X		X			X		X		X		X	
PHYSICAL EXAM	X	X	X	X	X	X	X	X	X	X	X	X	X	X	
VITAL SIGNS	X	X	X	X	X	X	X	X	X	X	X	X	X	X	
PREGNANCY TEST (if applicable)	X		X		X			X	X	X		X		X	
PRIOR & CONCOMITANT MEDICATIONS	X	X	X	X	X	X	X	X	X	X	X	X	X	X	
SAFETY LABORATORY TESTS**	X	X	X	X	X	X	X	X	X	X	X	X	X	X	
SERUM CREATININE	X	X	X	X	X	X	X	X	X	X	X	X	X	X	
STUDY MEDICATION ADMINISTRATION (if applicable)		X	X	X	X	X	X	X	X	X	X	X	X	X	
EVEROLIMUS LEVEL (if applicable)			X	X	X	X	X	X	X	X	X	X	X	X	
TACROLIMUS LEVEL (if applicable)	X	X	X	X	X	X	X	X	X	X	X	X	X	X	
MYFORTIC LEVEL (if applicable)	X				X			X	X	X		X		X	
OTHER IMMUNOSUPP THERAPIES	X	X	X	X	X	X	X	X	X	X	X	X	X	X	
SUSPECTED ACUTE REJECTION RECORD	X	X	X	X	X	X	X	X	X	X	X	X	X	X	
HOSPITALIZATION RECORD			X	X	X	X	X	X	X	X	X	X	X	X	
DIALYSIS RECORD			X	X	X	X	X	X	X	X	X	X	X	X	
AE & INFECTION LOG			X	X	X	X	X	X	X	X	X	X	X	X	
SERIOUS ADVERSE EVENTS			X	X	X	X	X	X	X	X	X	X	X	X	
GRAFT LOSS			X	X	X	X	X	X	X	X	X	X	X	X	
END OF TREATMENT /END OF STUDY														X	

** Safety Labs include: Chem 13; AST, ALT, CBC w/ Diff; Lipid Profile; Magnesium, Inorganic Phosphate

References

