The following data is in preparation for publication. Data was collected retrospectively for all patients transplanted between 3/14/2006 to 12/31/2007 at The University of Toledo Medical Center. There were *no exclusion criteria* other than limiting data to two transplant surgeons resulting in a study population of 143 patients. The first study group was given Prograf® (P) alone (47 patients) following transplantation, with the later group receiving Prograf® and myfortic® (P/M) (96 patients). Prograf® target level was 8 -12 ng/ml for both groups and myfortic® target dose was 720 mg PO bid adjusted for diarrhea and leukopenia. All patients were treated with Valcyte® and Bactrim® prophylaxis for 6-12 months. Review of the study populations showed no significance differences between the two immunosuppression groups for demographic details, death censored graft survival, patient survival, graft survival, rejection rate, one or two year creatinine level, severity of rejection (Banff score) or humoral rejection. Death censored graft survival rates after one year were 97.8% (P) and 89.4% (P/M). Two year death censored graft survival was 88.9% (P) and 85.6% (P/M). One year patient survival was 93.6% (P) vs 95.8% (P/M) and two year patient survival was 93.6% (P) vs 90.6% (P/M). Creatinine level at one year was 1.7±1.2 mg/dL (P) and 1.5±0.6 mg/dL (P/M) and at two years was 1.7±1.3 mg/dL (P) and 1.5±0.4 mg/dL (P/M). One year overall biopsy-proven rejection rates were 21.3% (P) vs 15.6% (P/M) and two year overall biopsy-proven rejection rates were 25.5% (P) vs 19.8% (P/M). Though not achieving statistical significance, our analysis demonstrated a trend toward differences in response to therapy based on ethnicity. At two years, rejection rates were 22.6% for Caucasians in both study groups, whereas in African-Americans, rejection rates were 45.5% (P) and 13% (P/M) (p=0.0789). While observing a 45% rejection rate in African-Americans treated with Prograf® in the absence of myfortic®, this increased rejection rate did not correspond to worsening two year graft survival that was 90.9%. Like the Miami experience, our data suggests caution with Campath® induction in African Americans, with two caveats: 1) our increased rejection rates were only seen in the absence of myfortic®; and 2) in the Miami study their results were limited by lower Prograf® bioavailability in African Americans.

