It is now clear that immunosuppressive strategies for renal transplantation achieve excellent short-term and medium-term results. Unfortunately, the long-term results have not substantially improved in the last 20 years. The reasons for this failure to achieve better long-term results are complicated and include such things as allowing older and sicker people to be recipients, using poorer quality donor kidneys and the complications associated with long-term immunosuppression. Among the worst of the long-term effects of chronic immunosuppression are the nephrotoxicity of the calcineurin inhibitors and the myriad complications of steroids. The goal of many now in the transplant field is to limit the exposure of transplant recipients to both steroids and calcineurin inhibitors. The following protocol evaluates the reduction of calcineurin inhibitors in a protocol that has already successfully eliminated the long-term use of steroids. Given the substantial experience with Campath® detailed above, the following study protocol will be offered to all patients undergoing renal transplantation at the University of Toledo University Medical Center. This is a small pilot study; multiple comparisons will be made for descriptive purposes only.

Hypothesis:

Our hypothesis is that conversion to everolimus (Zortress®), allowing the reduction of calcineurin inhibitors, will reduce nephrotoxicity (measured by increased creatinine clearance) and lengthen overall graft survival (measured by 2-year graft survival).

Objectives:

1. The primary objective of the study is to compare the efficacy and the effects on renal function of calcineurin-inhibitor reduction with conversion at 2 months after transplantation to Reduced Dose tacrolimus/everolimus in adult renal transplant recipients. Efficacy will be defined using two co-primary endpoints.
 - a. A composite efficacy end point [treated biopsy-proven rejection (BPAR), graft loss, death or loss to follow-up].
 - b. Renal function at 24 months post transplantation using GFR as measured by the Modified Diet Renal Disease (MDRD) estimation.

2. Secondary objectives will be to:
 - a. Compare the safety and tolerability of the experimental arm compared to the historical control arm.
 - b. Compare the presence of proteinuria as defined by spot urine protein to creatinine ratio greater than 1.0 in the experimental arm to the historical control arm.

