 - Adequate barrier methods of contraception include: diaphragm, condom (by the partner), intrauterine device (copper or hormonal), sponge or spermicide. Hormonal contraceptives include any marketed contraceptive agent that includes an estrogen and/or a progestational agent. Acceptable contraception methods will be discussed with all women of child-bearing potential.

- Reliable contraception should be maintained throughout the study and for 8 weeks after study drug discontinuation. For women who become pregnant while using Myfortic® or within 8 weeks of discontinuing therapy, we will report the pregnancy to the Mycophenolate Pregnancy Reference Registry ([name]) and will strongly encourage the patient to enroll in the pregnancy registry.
- Women are considered post-menopausal and not of child bearing potential if they have had 12 months of natural (spontaneous) amenorrhea with an appropriate clinical profile (e.g. age appropriate, history of vasomotor symptoms) or six months of spontaneous amenorrhea with serum FSH levels > 40 mIU/mL and estradiol < 20 pg/mL] or have had surgical bilateral oophorectomy (with or without hysterectomy) at least six weeks ago. In the case of oophorectomy alone, only when the reproductive status of the woman has been confirmed by follow up hormone level assessment is she considered not of child bearing potential.

Study Duration:

We plan to enroll 11 patients per year. Given this assumption, the enrollment will take five years. Adding two years of follow-up care, we will be able to complete the study in 7 years.

Study Design:

1. Single center pilot study utilizing historical control
2. A single treatment arm
3. Eleven patients per year
4. Five years to enroll 55 patients.
5. Enroll all patients who meet the inclusion criteria at 2 months and up to 6 months (± 10 days) post kidney transplantation and are willing to consent for this trial.
6. Patients would have study visits, serum creatinine measurements and other clinically relevant parameters measured monthly until 6 months, then q3 months until 2 years post-transplantation.
7. Graft survival would be measured by the absence of the need for dialysis.
8. It would not be mandatory, but a renal biopsy would be recommended at 2 years to look for underlying early signs of calcineurin toxicity/chronic allograft nephropathy.

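### The 24-month GFR co-primary has no rule for death or graft loss, so by default it compares only patients alive with a working graft and can hide harm

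*Combined protocol and SAP*

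**What the plan says.** Objectives, item 1, names two co-primary endpoints. The first is "A composite efficacy end point [treated biopsy-proven rejection (BPAR), graft loss, death or loss to follow-up". The second is "Renal function at 24 months post transplantation using GFR as measured by the Modified Diet Renal Disease (MDRD) estimation".

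The Statistical Section doubts whether the numbers allow the investigators usefully to "apply analysis of (co)variance for the statistical evaluation of a continuous variables such as creatinine clearance", and says they will try. I take this to cover MDRD GFR, because no other method is named for a continuous outcome. The same section plans Kaplan-Meier and Cox analyses of graft survival.

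Four other places bear on patients who leave the GFR comparison:
- Study Design, item 7, defines graft survival by freedom from dialysis.
- Study Design, item 11, lists death among the ways a patient may be counted as discontinued.
- Item 17 of the detailed management protocol applies intention-to-treat to biopsy-proven rejection only.
- The visit schedule has serum creatinine at every visit to month 24, with separate dialysis and graft-loss records.

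None of them says how a death or a graft loss enters the GFR comparison.

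On status, Study Purpose and Rationale says "multiple comparisons will be made for descriptive purposes only", and the Statistical Section says of the study that "it is not powered to achieve statistical significance".

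**The concern.** A GFR at a fixed late time describes the graft only in someone who is alive and still has it. An ANCOVA with no rule for the others omits the deaths. For graft losses it either omits them or uses a creatinine drawn on dialysis, which does not measure the graft. Those omitted are among the worst outcomes the trial can produce.

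The hypothesis is that the new regimen improves renal function and lengthens graft survival. If the regimens differ in graft loss or death, the two groups left in the GFR comparison have been filtered differently, and their mean difference no longer describes the effect in everyone converted. The Statistical Section intends the results for publication and meta-analysis whatever they show, so a distorted estimate would be carried forward even though the trial is only descriptive.

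**Working it through.** **1. The plan's own figure.** Study Design gives "Five years to enroll 55 patients" at eleven per year: 11 x 5 = 55, which reproduces. It is an accrual target. No alpha, power, effect size or GFR standard deviation is given. About 50-55 historical controls are expected.

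**2. How many patients could be affected.** The only local figures are in Background and Preliminary Data, for the tacrolimus/myfortic group (P/M, 96 patients transplanted in 2006-2007):
- Two years: "Two year death censored graft survival was 88.9% (P) and 85.6% (P/M"; "two year patient survival was 93.6% (P) vs 90.6% (P/M".
- One year, P/M: patient survival 95.8%, death-censored graft survival 89.4%.

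Assuming the two are independent, the share alive with a working graft is:
- one year: 0.958 x 0.894 = 0.856
- two years: 0.906 x 0.856 = 0.776
- unrounded difference: 0.081

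As a share of those with a working graft at one year, 0.081 / 0.856 = 9.4%. Applied to 55 patients, 0.094 x 55 = 5.2, or about 5.

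Cross-check without independence: counts that fit the rounded percentages are 84 of 96 working at one year and 77 of 96 at two years. The loss is 7 / 84 = 8.3%, or 4.6 of 55. These counts are inferred, and the one-year count is not the only fit.

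**3. What a survivors-only mean can do.** The inputs here are assumptions, not figures from the documents: underlying GFR with mean 50 and SD 18 in both arms, and graft loss or death in 10% of controls and 20% of the experimental arm.

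- *Losses unrelated to GFR.* Survivors-only difference (experimental minus control): 50 - 50 = 0. With losses scored as 0: 0.80 x 50 - 0.90 x 50 = -5.0 mL/min/1.73 m².
- *The lowest GFRs are lost.* The mean above a cut that removes a fraction p is 50 + 18 x φ(z) / (1 - p), where φ(z) is the normal density at the cut. Control: 50 + 18 x 0.1755 / 0.90 = 53.5. Experimental: 50 + 18 x 0.2800 / 0.80 = 56.3. Survivors-only difference: +2.8. With losses scored as 0: 0.80 x 56.3 - 0.90 x 53.5 = -3.1.
- *Losses partly related to GFR* (simulated): +2.0 survivors-only, -3.7 with losses scored as 0.

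With 8% against 16% lost, the survivors-only difference runs from 0.0 to +2.3, and the difference with losses scored as 0 runs from -4.0 to -2.3.

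So unequal losses alone are enough to hide harm. A result favouring the arm with more losses needs the further condition that low-GFR patients are the ones lost. Scoring losses as 0 serves only to show the effect here; the fix does not use it.

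**4. Would the separate event comparison reveal it?** With 55 per arm and a two-sided 5% test, power to detect 10% against 20% is 31%, and 25% for 8% against 16%. The plan disclaims power, so this is no fault in itself. It does mean that an unremarkable event comparison would give little reassurance beside a favourable GFR.

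**The case against.** The strongest reply is that nothing is lost from the trial. Co-primary a counts graft loss and death, graft survival has its own time-to-event analysis, and the whole exercise is a descriptive pilot against an unmatched historical control. This stands: a reader might infer that harm would vanish from the report, and the documents do not support that. But co-primary a pools these events with treated rejection and loss to follow-up, and no rule says how the two co-primaries are read together.

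Second, the plan nowhere restricts the GFR analysis to survivors, and its ANCOVA is tentative. That is also correct. The gap is silence, and the survivors-only comparison is what the default would produce.

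Third, a reader might take 1 - 0.776 = 22%, or about 12 of 55, as the share without a usable value. That figure should not be used. It counts losses from transplantation in a cohort with essentially no exclusions. Trial patients and controls must reach 2-6 months with a working graft, no rejection, serum creatinine below 2.5 mg/dL and eGFR of at least 30, so losses before enrolment cannot occur in this comparison.

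Fourth, ranking death below every GFR changes the question from nephrotoxicity towards a composite. This is fair, and is why the rank analysis belongs beside the ANCOVA rather than in its place.

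**Conclusion.** The point holds as a gap in the definition and analysis of co-primary b. By default the comparison is among patients alive with a working graft. It can hide harm if the arms differ in graft loss or death, and it can favour the arm with more losses if those lost had low GFR. The documents establish neither the size nor the direction for this trial.

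The figure of about 9%, or 5 of 55, is a rough guide only. It assumes independence, comes from an unselected cohort under an earlier steroid regimen, and leaves out losses between enrolment and month 12. Selection at entry pulls the true figure down; the omitted months push it up.

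A reader might also infer that the centre's data already show survivor bias, since two-year creatinine looks better on P/M than on tacrolimus alone (1.5 against 1.7 mg/dL) while patient and graft survival look worse. The document reports none of these differences as significant and does not say who contributed creatinine values, so the pattern is compatible with such bias but does not demonstrate it.

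Because the trial is descriptive, the consequence is a misleading estimate, not a false confirmatory claim.

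**What to change.** Add to the Statistical Section:
- An all-patient comparison of 24-month GFR that ranks death and graft loss below every observed value. Make it rank-based and adjust for eGFR at the 2-6 month eligibility assessment in both groups. State how that value is chosen for historical controls, who had no enrolment visit.
- The ANCOVA in patients with a working graft, reported beside it in mL/min. MDRD values obtained on dialysis are not used as graft function.
- The number excluded per arm, by reason: death, graft loss, withdrawal or loss to follow-up.
- A statement that living patients with a missing value are treated as missing and reported separately, not ranked worst.
- A statement that no renal-function benefit will be claimed from the survivors-only result if the all-patient result does not agree in direction.

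The cost is a few sentences and one more analysis. No new data should be needed: eGFR is an entry criterion, and Study Design, item 10, applies the same criteria to the controls. The drawback is that the rank result is not in mL/min; the ANCOVA beside it keeps that scale. This is a cheap improvement.
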